Adverse events will be based on serious adverse events (SAE) case report forms. A serious adverse event is defined as any adverse event or adverse reaction that results in death, is life-threatening, requires hospitalisation or prolongation of existing hospitalisation, results in persistent or significant disability or incapacity, or is a congenital anomaly or birth defect. The following summaries will be presented as overall rates and stratified by AE classification:

[figure not shown]
- the number and percentages of patients reported as having Serious Adverse Events (SAE) in each treatment group; and,
- the number and percentages recorded as having all forms of Adverse Events (AE) in each group.

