12.3 Harms (safety assessments)

12.3.1 Serious Adverse Events

Trial sites are to report SAEs in conjunction with the CTRU standard operating procedure PM004 (Adverse events and serious adverse events). The definition of an SAE is as follows:

- results in death;
- is life-threatening* (subject at immediate risk of death);
- requires in-patient hospitalisation or prolongation of existing hospitalisation;**
- results in persistent or significant disability or incapacity;

- consists of a congenital anomaly or birth defect; or,
- is another important medical event that may jeopardise the subject.***
- * 'life-threatening' refers to an event in which the patient was at risk of death at the time of the event; it does not refer to an event which hypothetically might have caused death if it were more severe.
- **Hospitalisation is defined as an inpatient admission, regardless of length of stay, even if the hospitalisation is a precautionary measure for continued observation. Hospitalisations for a pre-existing condition, including elective procedures that have not worsened, do not constitute an SAE.
- ***Other important medical events that may not result in death, be life-threatening, or require hospitalisation may be considered a serious adverse event/experience when, based upon appropriate medical judgment, they may jeopardise the subject and may require medical or surgical intervention to prevent one of the outcomes listed in this definition.

It is not anticipated that there will be many SAEs related to the behaviour change intervention. We will report any SAEs which are deemed related to the trial intervention and unexpected to the Sponsor within the specified timeframes below (12.3.4).

12.3.2 Adverse events we require reporting:

We do require that sites report any new diagnosis of depression and/or anxiety which requires treatment with medication or psychological therapy e.g. Cognitive Behavioural Therapy (CBT).

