12.3.4 Reporting

Adverse events and SAEs can be reported for participants at any stage of their trial participation. A member of the site study team (interventionist, clinician or other) will enquire about any adverse events at routine clinic appointments. These will be record on the adverse event section of the paper CRF and database. The event will be assessed by the local Principal Investigator and the form will be kept in the site file. Serious adverse events will be reported in the periodic safety reports to the research ethics committee and Trial Steering committee.

All adverse events (serious or other based on the definitions above) will be recorded on the case report form and details will be **entered on the study database within 1 week of completing the paper form**. Any SAEs which are deemed related to the trial intervention, the site will complete the paper CRF and **fax this form to the CTRU within 24 hours of becoming aware of the event** in order for the CTRU to report this event to the Sponsor and the main REC within the required timeframes (15 days).

•

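### Section 11.1 names SAE forms as the source of adverse events, which cannot supply its own by-arm summary of all adverse events and conflicts with section 12.3.4

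*Protocol*

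**What the plan says.** Section 11.1 of the protocol gives one data source for harms: "Adverse events will be based on serious adverse events (SAE) case report forms". It then defines a serious adverse event by five criteria and plans two summaries, to be shown overall and by event classification:

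- a count, with percentages, of patients who had a serious event, by treatment arm;
- for events of every kind, "the number and percentages recorded as having all forms of Adverse Events (AE) in each group"

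Section 12.3 describes what sites report and where it goes. Section 12.3.1 lists six SAE criteria; the one absent from 11.1 reads "is another important medical event that may jeopardise the subject". Section 12.3.2 adds a specific requirement: "We do require that sites report any new diagnosis of depression and/or anxiety which requires treatment with medication or psychological therapy". It attaches no condition of seriousness. Section 12.3.4 says "A member of the site study team (interventionist, clinician or other) will enquire about any adverse events at routine clinic appointments", then "These will be record on the adverse event section of the paper CRF and database", and later "All adverse events (serious or other based on the definitions above) will be recorded on the case report form", with entry on the study database to follow.

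**The concern.** The analysis section and the reporting section disagree about where adverse events come from. Section 12.3.4 sets up collection of serious and other events. Section 11.1 then points the analyst to the serious ones only, while promising a table that needs both.

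The event most exposed is the one the protocol singles out. A new diagnosis of depression or anxiety treated with medication or talking therapy will often meet none of the SAE criteria, so it would not be expected on an SAE form. The protocol considered this event important enough to require its reporting in a trial that feeds adherence data back to patients. A table built from SAE forms could not show a difference between arms in its non-serious cases.

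The final table also matters because little else in the protocol compares these events by arm. Section 12.1 does not convene a data monitoring committee, section 12.2 plans no interim analysis, and the periodic safety reports in 12.3.4 are described only for serious events.

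**Working it through.** No figure in the protocol bears on this point and there is nothing to recompute. The check sets the passages side by side.

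1. **Source.** 11.1: SAE case report forms. 12.3.4: the adverse event section of the paper CRF and the database, for serious and other events alike. The second source is wider than the first.

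2. **Planned output.** 11.1 asks for patients with SAEs by arm and, as a separate item, all forms of adverse event by arm. Let S be the patients in an arm with at least one SAE, and N those with at least one non-serious event. The first summary counts S. The second should count S ∪ N.

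3. **Source applied to output.** With SAE forms as the only source, N is not observed and the second summary counts S again. The two summaries coincide. The shortfall in patients is |S ∪ N| − |S|, that is, those with non-serious events only. A patient in both S and N stays in the count but loses the non-serious event from the breakdown by classification.

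4. **Where the required event falls.** 12.3.2 makes treatment, not seriousness, the trigger for reporting new depression or anxiety. A case that leads to admission, or otherwise meets 12.3.1, is in S and would be on an SAE form. A case managed without meeting any of those criteria is in N only and would not be. The literal reading therefore loses the non-serious cases, not every case.

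5. **Whether the data would exist.** Under 12.3.4 they would. Staff ask about any adverse event at routine clinic appointments, and events are recorded and entered. The fault lies in the source named for analysis, not in collection.

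6. **SAE definition.** 11.1 gives five criteria: death, threat to life, hospitalisation, disability and congenital anomaly. 12.3.1 gives these plus other important medical events, making six. The two texts differ and should be aligned.

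7. **Size.** The shortfall in step 3 needs rates of non-serious events, and of depression or anxiety, by arm. The protocol gives none.

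**The case against.** The strongest reply is that the source sentence is loosely worded and the rest of the protocol makes the intention plain. Section 11.1 lists an all-event summary separately from the SAE summary, by group and by classification, and 12.3.4 collects the data for it. A statistician would probably follow the explicit deliverable. This stands as far as certainty goes: the events are lost only if the source sentence overrides the summary below it, and the protocol does not settle which governs. It does not remove the contradiction, because one of the two statements has to give way.

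A second reply is that depression and anxiety are compared by arm anyway. PHQ-8 and GAD-7 are secondary outcomes, analysed in 11.1 by regression on baseline value and group with 95% confidence intervals. That is a real safeguard and lowers the stakes. It is not a substitute. The scales are scheduled at consent and at 12 months, so an episode diagnosed, treated and resolved in between may leave no trace, and a score is not a treated new diagnosis.

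Three stronger readings are tempting and should not be drawn:

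- **All depression and anxiety events would be lost.** Serious cases would be on SAE forms, and the non-serious ones are lost only on the literal reading.
- **SAEs qualifying only as other important medical events would go uncounted.** Sites report under the six criteria of 12.3.1, and 11.1 counts patients reported as having SAEs. Nothing says that the forms are screened again against the shorter list.
- **SAEs are collected only at 12 months, because Table 3 marks other SAEs there.** That mark fits a final check, 12.3.4 allows reporting at any stage, and the table is damaged in the text available.

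A separate row for depression and anxiety, or a particular table label, is a matter of presentation that the SAP may settle.

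**Conclusion.** The concern holds as an inconsistency in a stated rule. Section 11.1 names a source for adverse events that cannot support its own all-event summary and that conflicts with 12.3.4. If followed as written, it would leave non-serious events out of the by-arm table, including non-serious cases of the new treated depression or anxiety that 12.3.2 requires sites to report.

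This rests on two assumptions: that SAE case report forms means forms for serious events only, distinct from the adverse event section of the CRF, which the wording suggests but does not state outright; and that the source sentence is applied literally. The number of events at risk cannot be estimated from the protocol. The primary outcome and its analysis are not affected. Severity is minor to moderate. The five-criterion definition is a drafting mismatch to tidy at the same time, with no demonstrated loss of events.

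**What to change.** In 11.1, replace the source sentence with one stating that adverse event summaries are derived from the adverse event section of the CRF and study database together with the SAE forms. The all-event summary will then differ from the SAE summary as intended, and the depression and anxiety events required by 12.3.2 will be tabulated by arm. Replace the restated SAE definition in 11.1 with a reference to 12.3.1, so that one definition governs both reporting and analysis.

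The cost is a line or two of text, best agreed before data lock. No new data are needed, since 12.3.4 already provides for their collection and entry.

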11.3 Combining data and findings from the different components

We will use Farmer's triangulation protocol to display the findings from each component of the study together and discuss as a team the extent to which findings converge, complement each other or contradict each other [59, 60]. For example, we will display all findings about acceptability of the intervention.

12. Monitoring

12.1 Oversight

The CTRU SOP GOV003 Data Monitoring and Ethics Committee states "A DMEC does not need convening in studies that carry low risk to patients". This project involves delivering a behaviour change intervention through the website CFHealthHub and would therefore be classified as low risk.

The overall responsibility for the study will be with Sheffield Teaching Hospitals NHS Trust who will act as sponsors for the study. The local Principal Investigator (PI) will be responsible for the study at each participating site and it will be registered and approved with each local R&D department. The study will be conducted in accordance with the protocol, GCP and Sheffield CTRU Standard Operating Procedures. The two committees which will govern the conduct of the study are:

- 1. Programme Steering Committee (PSC)
- 2. Project Management Group (PMG)

The PSC will be responsible for the overall conduct of the trial and consists of an independent chair and four other independent members including a statistician and PPI representative. The committee will meet every 6 months to monitor the study.

The PMG will comprise of the trial manager and the core research team. The PMG will meet on a monthly basis to monitor the day-to-day running of the trial. The Trial Manager will be jointly supervised by the CI and the Assistant Director of CTRU via the form of regular meetings (face to face and telephone calls). The Trial Manager will be responsible for liaising with the whole project team. Trial monitoring procedures will be assessed based on the level of risk of the study. The Site Monitoring Plan will outline the types and frequency of site monitoring activities for the study and this will be agreed with the Sponsor prior to the start of the study.

12.2 Description of any interim analyses and stopping guidelines

There are no planned interim analyses or stopping guidelines for this study.

12.3 Harms (safety assessments)

12.3.1 Serious Adverse Events

Trial sites are to report SAEs in conjunction with the CTRU standard operating procedure PM004 (Adverse events and serious adverse events). The definition of an SAE is as follows:

- results in death;
- is life-threatening* (subject at immediate risk of death);
- requires in-patient hospitalisation or prolongation of existing hospitalisation;**
- results in persistent or significant disability or incapacity;

- consists of a congenital anomaly or birth defect; or,
- is another important medical event that may jeopardise the subject.***
- * 'life-threatening' refers to an event in which the patient was at risk of death at the time of the event; it does not refer to an event which hypothetically might have caused death if it were more severe.
- **Hospitalisation is defined as an inpatient admission, regardless of length of stay, even if the hospitalisation is a precautionary measure for continued observation. Hospitalisations for a pre-existing condition, including elective procedures that have not worsened, do not constitute an SAE.
- ***Other important medical events that may not result in death, be life-threatening, or require hospitalisation may be considered a serious adverse event/experience when, based upon appropriate medical judgment, they may jeopardise the subject and may require medical or surgical intervention to prevent one of the outcomes listed in this definition.

It is not anticipated that there will be many SAEs related to the behaviour change intervention. We will report any SAEs which are deemed related to the trial intervention and unexpected to the Sponsor within the specified timeframes below (12.3.4).

12.3.2 Adverse events we require reporting:

We do require that sites report any new diagnosis of depression and/or anxiety which requires treatment with medication or psychological therapy e.g. Cognitive Behavioural Therapy (CBT).

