The participant will be encouraged to set a realistic % adherence goal for the next four to six weeks and this will be recorded on CFHealthHub. The interventionist will support the participant to revise their action plan as needed and save this to the 'My toolkit' zone. Based on the earlier discussion about the barriers that prevented goal achievement the Problemsolving module on CFHealthHub will be used to address each of the problems encountered, and any that are anticipated. Relevant solutions will be saved to the 'My Toolkit' zone of CFHealthHub.

The visit will conclude with a review of the goal and the tailored and personalised contents saved to the 'My toolkit' zone of CFHealthHub. The interventionist will re-emphasise a learning mindset, emphasising that the participant cannot fail, but can learn from the process so that they can work together on the adherence challenge.

[figure not shown]
Participating centres will provide participants with contact details, typically telephone numbers, but other methods may be volunteered by centres. Contact details will be provided so that participants can contact the centre if they have queries or problems regarding CFHealthHub between visits. The interventionist will be able to feedback any information from the intervention delivery **after** the baseline intervention visit to members of the wider CF team. This may include adherence data from sessions with the participant's clinician and MDT particularly if the participant raises any concerns or issues e.g. side effects of a drug to allow their usual clinician to discuss this with them at their next clinic visit.

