12.3.3 Expected SAEs and adverse events

Certain adverse events are common to CF and associated medications. Expected SAEs must be reported in the annual safety report. Hospitalisation as a result of an exacerbation will be recorded in the study database and not be reported as an SAE.

Expected AEs in relation to medications or common in patients with CF

- 1. Acute FEV₁ drop >15% after 1st dose of medication
- 2. Increased productive cough
- 3. Nasal congestion or stuffy nose
- 4. Chest congestion
- 5. Wheezing
- 6. Chest pain or chest discomfort
- 7. Voice alteration/change
- 8. Dysponea (breathlessness)
- 9. Haemoptysis (coughing blood)
- 10. Rhinitis
- 11. Headache
- 12. Crackles in lung
- 13. Throat irritation/ sore throat
- 14. URTI
- 15. Sinusitis
- 16. Deafness

- 17. Indigestion / reflux
- 18. Tonsillitis
- 19. Joint pain
- 20. Decreased appetite
- 21. Fatigue
- 22. Headache
- 23. Distal intestinal obstructive syndrome
- 24. Fever
- 25. Otitis media or ear infection
- 26. Conjunctivitis
- 27. Pneumothorax
- 28. Decreased exercise tolerance
- 29. Pyrexia
- 30. Abdominal pain
- 31. Influenza
- 32. Pseudomonas infection
- 33. Vomiting
- 34. Diabetes
- 35. Pneumonia

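### The protocol gives conflicting scopes for non-serious adverse events, so its by-arm table of all adverse events could be incomplete or unevenly ascertained

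*Protocol*

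**What the plan says.** Five places in the protocol bear on which non-serious adverse events are collected and tabulated.

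- **Section 12.3.2**, on the adverse events that sites are required to report, names a single item: "We do require that sites report any new diagnosis of depression and/or anxiety which requires treatment with medication or psychological therapy".
- **Section 12.3.3** has a list of 35 numbered entries under the line "Expected AEs in relation to medications or common in patients with CF". It does not say whether the non-serious ones are to be recorded.
- **Section 12.3.4** provides for open enquiry: "A member of the site study team (interventionist, clinician or other) will enquire about any adverse events at routine clinic appointments". It continues: "These will be record on the adverse event section of the paper CRF and database". The next paragraph says: "All adverse events (serious or other based on the definitions above) will be recorded on the case report form". The section also allows events to be reported throughout participation.
- **Table 3 (section 7.4) and Figure 6** set out what is collected and when. The only general safety item in either is other SAEs, placed at 12 months. Neither shows an adverse event item at routine clinic visits.
- **Section 11.1** says "Adverse events will be based on serious adverse events (SAE) case report forms", and then promises "the number and percentages recorded as having all forms of Adverse Events (AE) in each group".

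Three design features matter as well. Under section 9.4 only the statisticians are blinded. Under section 6.4.4.4 only the CFHealthHub group has review sessions with the interventionist. Section 6.4.4 also lets the interventionist pass information from those sessions to the clinical team, particularly if the participant "raises any concerns or issues e.g. side effects of a drug".

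**The concern.** The intervention works by raising adherence to inhaled drugs (section 6.4.1). If it succeeds, exposure to those drugs rises in one arm, and section 12.3.3 itself recognises adverse events linked to medication. A by-arm adverse event table is where a reader would look for a cost of that extra exposure.

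Such a table is informative only if the same events are sought in the same way in both arms. Here a site could follow 12.3.2 and record one diagnosis, or follow 12.3.4 and record everything. It could also work from Table 3 and record no non-serious adverse events at clinic visits. Counts would then depend on which passage a site follows and, where recording is discretionary, on how much contact the participant has with unblinded staff. A sparse table might be taken as reassurance, and an excess in the intervention arm might reflect only more conversations.

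Sections 12.1 and 12.2 plan no data monitoring committee and no interim analysis, so the summaries in 11.1 are the main planned by-arm comparison of harms.

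**Working it through.** No arithmetic applies: the protocol gives no adverse event rate, and the point turns on what is collected. The check is to compare the passages.

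**Step 1: which non-serious events are in scope?**
- 12.3.2: new treated depression or anxiety.
- 12.3.4, enquiry sentence: any adverse event.
- 12.3.4, recording sentence: all adverse events, qualified by the definitions above it. Read narrowly, this points to 12.3.2, the only non-serious category that the text above says must be reported. Read broadly, it also takes in the 12.3.3 list. The text does not settle which.
- 11.1: all forms of adverse event.

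These range from one diagnosis to everything.

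**Step 2: when are they collected?**
- 12.3.4: by enquiry at routine clinic appointments, with reporting possible at any stage.
- Table 3: other SAEs at 12 months.
- Figure 6: the clinic-visit data are FEV1, the subjective adherence question, the exacerbations form, EQ-5D-5L and the behavioural questionnaire. Other SAEs appear at the 12-month visit.

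The enquiry described in 12.3.4 is in neither schedule. A site working from the schedule would not be prompted to make it.

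**Step 3: from which form is the table built?**
- 12.3.4: events found on enquiry go on the adverse event section of the CRF and into the database.
- 11.1: summaries are based on SAE case report forms.

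A count of all forms of adverse event cannot come from SAE forms alone, because non-serious events are not SAEs. Section 11.1 conflicts with itself here, and with 12.3.4.

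**Step 4: is ascertainment even between arms?**
- The clinic-visit enquiry is worded without restriction by arm, so it is a source common to both.
- Reporting is also open at any other time, to staff who know the allocation.
- Only the intervention arm has interventionist sessions, and drug side effects are given as an example of what may be raised there.

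The protocol does not require events to be recorded by source. If events first mentioned in a session reach the CRF, they cannot be separated from those found by the common route.

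**The case against.** The strongest reply is that 12.3.4 already answers the point. Staff ask about any adverse event at routine clinic visits, with no limit by arm or event type, and enter what they find on the CRF and database. A reader of 12.3.2 alone might infer that treated depression or anxiety is the only non-serious event sites must record, and that drug-related events go uncollected. The document does not support that: 12.3.4 is wider on its plain wording, and the 12.3.3 list also stands above the phrase about definitions.

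A second reply is that the arm imbalance is inferred. The feedback of side effects in section 6.4.4 is a clinical route, so that the usual clinician can discuss them at the next clinic visit. It is not described as a way of recording adverse events. That is correct, so imbalance is a possibility the plan leaves open and not one it states.

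Third, the trial has other information on harm in both arms: SAEs, FEV1, CFQ-R, EQ-5D-5L, PHQ-8, GAD-7 and concomitant medication. Interviews also cover perceived harms. This too is correct, so it would be wrong to say that the trial cannot weigh benefit against harm.

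None of these replies removes the conflict. The enquiry in 12.3.4 is missing from both data schedules, its scope is qualified in the next paragraph, and 11.1 names the wrong form for the table it promises. A statistical analysis plan could correct the source named in 11.1, but not what sites were told to collect.

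**Conclusion.** The concern holds as an internal contradiction about collection and reporting. Sections 12.3.2, 12.3.4 and 11.1, with Table 3 and Figure 6, give different scopes, times and source forms for non-serious adverse events. Followed as written, they could produce a table of all adverse events by arm that is incomplete, differs by site, or is ascertained more fully in one arm.

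Its size cannot be stated. The protocol gives no adverse event rates and no figure for how often events surface in intervention sessions, and any power calculation for drug-related events would rest on invented inputs. The direction of a bias is also uncertain. More contact would tend to inflate counts in the intervention arm. Many entries in 12.3.3, such as haemoptysis, breathlessness, fatigue and fever, overlap the signs of exacerbation in section 7.1.1 and might fall if the intervention works.

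A reader might go further and conclude that the trial cannot show drug-related harm. The documents do not support that, because an enquiry common to both arms is described. The conclusion assumes that sites would act differently on the conflicting passages; a CRF or site manual not shown here might already give a single rule.

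**What to change.** Reconcile sections 11.1 and 12.3.2 to 12.3.4, Table 3 and Figure 6 so that one stated scope of non-serious adverse events applies to both arms. In particular:

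- add the clinic-visit enquiry of 12.3.4 to Table 3 and Figure 6;
- replace the reference to definitions above in 12.3.4 with an explicit statement of what is recorded;
- amend 11.1 so that the table draws on the adverse event section of the CRF as well as the SAE forms;
- record whether each event arose at a routine clinic visit or an intervention session;
- base the by-arm comparison of non-serious events on the clinic-visit source, and label the table with its scope and source.

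A mandatory checklist of the 12.3.3 entries is not needed for this. That list mixes medication effects with common features of CF and does not separate them.

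The cost is a wording amendment, one source field on the CRF and modest extra data entry. The enquiry is already planned at existing visits, so no new visits are required.
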